### **3.3. Exploratory Endpoints**

*Exploratory Aim 1: Assess whether sensor-based baseline measures can stratify treatment response*

**Wearable sensor metrics** from 3.1 A (Table 1 Column 1); 3.1 B (Table 2 Column 1) and 3.1 E. As described in the analysis Section 4 below, only a subset of these endpoints that show excellent agreement with the gold standard measures during in-lab assessments (ICC  $\geq 0.75$ ) will be investigated for this aim.

ePRO endpoints listed in Section 3.2.

*Exploratory Aim 2: Assess whether participant phenotype; pain, physical performance, affective traits (catastrophizing), can stratify treatment response*

Physical Performance Endpoints listed in Section 3.1D and ePRO endpoints in Section 3.2.

Pain phenotyping endpoints

- PPT (kgf)
- Temporal summation (yes/no)
- CPM (yes/no)
- EIH (yes/no)
- Number of painful joints from joint homunculus
- Pain catastrophizing (modified)
- Widespread pain (single question)
- PainDETECT (modified)

Strength assessment endpoints:

- Isometric testing

- Peak extensor torque (Nm/kg)
- Peak flexor torque (Nm/kg)
- Isokinetic testing
  - Peak extensor torque at 60 deg/s (Nm/kg)
  - Peak flexor torque at 60 deg/s (Nm/kg)
  - Peak extensor torque at 120 deg/s (Nm/kg)
  - Peak flexor torque at 120 deg/s (Nm/kg)

### 3.4. Substudy Endpoints

*Substudy Aim 1: Examine the test-retest reliability of at-home instrumented physical performance tests*

*Substudy Aim 2: Examine agreement between wearable sensor data collected during in-lab and at-home instrumented physical performance tests*

**Table 3. Gait measures obtained from GaitPy algorithm applied on the lumbar sensor and from 3-sensor IMU System during the 7-meter walk tasks performed at home and in-lab**

	GaitPy applied on Lumbar Sensor 	3-sensor IMU system 
a.	Cadence (steps/min)	Cadence (steps/min)
b.	Step length symmetry	
c.	Gait speed (m/s)	Gait speed (m/s)
d.	Stride duration (s)	Gait cycle duration (s)
e.	Stride duration asymmetry (s)	
f.	Step duration (s)	Step duration (s)
g.	Step duration asymmetry (s)	
h.	Initial double support time (s)	
i.	Terminal double support time (s)	Terminal double support (% gait cycle, s)
j.	Total double support time (s)	Double support (% gait cycle, s)
k.	Single limb support time (s)	
l.	Stance time (s)	Stance phase (% gait cycle, s)
m.	Swing time (s)	Swing (% gait cycle, s)
n.	Step length (m)	
o.		Foot clearance (m)
p.		Lateral step variability
q.		Foot strike angle (deg)

r.		Toe off angle (deg)
s.		Toe out angle (deg)
t.		Turning angle (deg)
u.		Turning duration (s)
v.		Turning velocity (deg/s)

**Table 4. Sit-to-stand measures derived from Sit2StandPy algorithm applied on the lumbar sensor and from the 3-sensor IMU system during the 5 times sit-to-stand tasks performed at home**

	Sit2StandPy applied on Lumbar Sensor	3-sensor IMU system^16
a.	Number of sit-to-stands	
b.	Sit-to-stand duration (s)	Sit-to-stand duration (s)
c.	Maximum acceleration (m/s  )	
d.	Minimum acceleration (m/s  )	
e.	SPARC: SPectral ARC length	
f.		Stand-to-sit duration (s)

### 3.5. Safety Endpoints

An AE is defined as any untoward medical occurrence and can therefore be any unfavorable and unintended sign (including an abnormal laboratory finding), symptom, or disease, whether or not related to the participant's participation in the study.

Any AE that occurs from the time the participant consents to the clinical research through the completion of the qualifying procedure will be recorded.

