2.3. Benefit/Risk Assessment

Participants may benefit from receiving PT as it is currently standard of care for management of OA of the knee, and generally recommended as first-line therapy for all patients with knee OA. No other personal benefits are expected from participating in this study. The information collected in this study will be useful in developing better ways to assess the impact of exercise and strength therapy in knee OA. Hence, the overall goal is to improve the quality of information available to physicians treating patients with knee OA and to researchers developing new therapies for OA.

Intervention risks: In some persons, knee pain could worsen with exercise. To reduce this risk, participants will receive a supervised and standardized knee OA specific exercise protocol, with individualized progression across participants by a physical therapist member of the study team.

Wearable sensor risks: There is the possibility of skin irritation and discomfort with continued wearable device use. In case of discomfort or skin irritation, participants will be instructed to remove the device on their own.

Motion analysis risks: There are no known side effects from being filmed by high speed cameras. Since the participants will be asked to perform walking, stair climbing type activities, as with any such activity, there is a risk that they may lose balance, stumble, fall, and experience an injury. There is a risk of slight discomfort with the skin shaving and cleaning with the alcohol swab before placing the EMG sensors. All participants will observe a demonstration of the movement and will be able to perform a few practice trials to become familiar with each activity prior to data collection. The testing area will be well lit and clear of any obstacles. The participants will be provided ample rest breaks. They will be encouraged to perform each activity at a rate that they feel comfortable. If they show signs of shortness of breath, testing will be stopped immediately, and they will be allowed to rest. The participants will be explained the process of placing the EMG sensors. If a participant expresses discomfort with the shaving or cleaning, the process will be stopped and the sensors will be placed without the skin preparation.

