6. STUDY INTERVENTION AND ASSESSMENTS

6a. MAIN STUDY

Recruitment and screening:

Participants will be recruited through multiple channels (flyers, newspaper advertisements, clinical data warehouse, etc.) including via social media using Trialfacts. Screening will occur via a 4-step process. Step 1 will be online pre-

screening using Trialfacts screening webpage. Those eligible will then undergo telephone pre-screening as step 2. Step 3 would be obtaining confirmation of knee OA diagnosis from the participant's physician along with clearance to participate in an exercise program. Step 4 will be an in-lab visit (part of baseline visit) to confirm BMI eligibility. If in-lab screening visit is not possible due to COVID-19, BMI eligibility will be determined from the physician diagnosis letter that includes a most recent height and weight.

COVID-19 Screening: Prior to all in-lab and in-clinic visits, participants will be screened for potential exposure to COVID-19 using BU mandated protocols. Participants will be called prior to their visit to determine if they have any COVID-19 related symptoms, if they have been in close contact with a known or suspected COVID-19 positive case, request they take their temperature prior to their appointment, and inform participants to call the lab/clinic if they develop any COVID related symptoms prior to their visit. In addition, participants will undergo symptom and temperature screen in person when they arrive for lab/clinic visits. Participants will be required to wear a face mask during the entire visit and perform hand hygiene before entering the lab. This screening will remain in place until Boston University guidelines recommend discontinuation of its use.

Informed consent: Most participant consents will be completed in-person during the baseline in-lab visit. For participants in the substudy randomized to completing the baseline at-home visit prior to the baseline in-lab visit (n=6-10), the informed consent will be obtained during an additional in-lab visit specifically for BMI screening, obtaining consent and providing tablet computer and sensors. If the in-lab visit is not possible due to COVID-19 related restrictions, the informed consent will be obtained remotely via REDCap and video call.

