Intervention: The intervention will consist of an exercise-based physical therapy program for 12 weeks. The intervention will also include pain education and manual therapy as needed. There will be two visits per week for the first 6 weeks and one visit per week for the next 6 weeks. The table below shows which visits will be in-clinic (IC) vs. tele-health (TH) and clinical assessments during the intervention. After completing the PT program, participants will follow an exercise plan at home from week 13 to 18.

If in-clinic intervention visits are not possible due to closure of the BU Physical Therapy Center for reasons related to COVID-19, they will be delivered via tele-health. However, the first physical therapy intervention visit will always be in-clinic.

Week	1	1	2	2	3	3	4	4	5	5	6	6	7	8	9	10	11	12
Intervention Visit	1	2	3	4	5	6	7	8	9	10	11	12	13	14	15	16	17	18
Visit Type	IC	IC	IC	IC	TH	TH	TH	TH	IC	IC	IC	IC	TH	TH	IC	TH	TH	IC
QUESTIONNAIRES																		
Exercise Adherence		DAILY																
KOOS	x	x	x	x	x	x	x	x	x	x	x	x	x	x	x	x	x	x
Pain (current, best, worst)	x	x	x	x	x	x	x	x	x	x	x	x	x	x	x	x	x	x
NPQ	x											x						x
GROC											x							x
Modified STarT Back	x																	
CSI	x																	
IPAQ	x																	
WAI			x															
CLINICAL ASSESSMENTS																		
Alignment	x																	
Gait	x																	
TUG	x																	

Single Limb Balance	x	As needed
Step performance	x	As needed
Sit to stand/squat performance	x	As needed
ROM	x	As needed
Joint Play	x	As needed
MMT	x	As needed
Muscle Length	x	As needed

Assessments: Participants will be asked to participate in 4 (four) laboratory assessments; 4 (four) week-long monitoring periods with a lumbar sensor throughout the study; and continuous monitoring with a wrist sensor throughout the study's duration. Additionally, participants will complete daily questionnaires (sleep interference, medication use, exercise and activity log) and weekly questionnaires for assessment of pain and physical function (ie, KOOS [pain and symptoms], PGA-OA, NRSna).

Visit #1 (Baseline Assessment; Week -1)

Participants will complete questionnaires (see table above) and undergo multiple assessments of gait, strength and function in the lab.

Measurements of vital signs (heart rate, blood pressure) will be performed including measurement of height and weight. If the baseline visit occurs at-home due to COVID restrictions vitals, height, and weight will not be performed.

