7. ANALYSIS PLAN

7.1. Analysis of Primary Aim and Endpoints

Details of the analysis of this study will be documented in the Statistical Analysis Plan (SAP). The analyses described in the approved SAP will be followed if different from what is described in this protocol.

Primary Aim: Measure the effect of PT on functional performance using digital measures from wearable sensors.

The following analyses will be performed to address this primary aim.

A. Validate wearable sensor-based metrics of functional biomechanical tests in people with knee OA against optical motion capture

Data from the lumbar sensor and optical motion capture during gait and sit-to-stand tasks during in-lab visits will be used for this analysis. Wearable sensor metrics will be compared against gold standard metrics from the optical motion capture system using intra-class correlation coefficient (ICC) and its 95% lower and upper confidence limits. The ICC reflects both the degree of correlation and agreement between the measurements. We will interpret agreement between measurements according to the following benchmarks: $ICC \leq 0.4$ indicates 'poor', 0.4 to 0.59 'moderate', 0.6 to 0.74 'good', and 0.75 to 1 'excellent' reliability (Cicchetti et al., 1994). In addition, we will also compute the mean, variance and percentage error between the standard and the digital measurements. Bland–Altman plots and 95% limits of agreement (average difference ± 1.96 standard deviation of the difference) will also be computed.

B. Compare wearable sensor-based metrics of physical performance in people with knee OA with standardized physical performance outcomes.

Wearable sensors with excellent reliability from analysis A will be examined. Sensor-based metrics from lumbar sensor during physical performance tests in-lab will be correlated with standardized physical performance outcomes using Pearson's product-moment correlations or Spearman's rank order correlations depending on their normality.

C. Assess the effects of exercise-based PT on outcomes from wearable sensors during in-lab physical performance tests

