9. CONSENT

The documents used during the informed consent process and any participant recruitment materials will be reviewed and approved by the study site institutional review board. The informed consent documents and any participant recruitment materials will be in compliance with local regulatory requirements and legal requirements, including applicable privacy laws. The investigator will ensure that each study participant is fully informed about the nature and objectives of the study, the sharing of data relating to the study and possible risks associated with participation, including the risks associated with the processing of the participant's personal data. The investigator further will ensure that each study participant is fully informed about his or her right to access and correct his or her personal data and to withdraw consent for the processing of his or her personal data.

The investigator, or a person designated by the investigator, will obtain written informed consent in-person from each participant before any study-specific activity is performed. The investigator will retain the original of each participant's signed consent document. The informed consent document will specify that the investigators will not attempt to connect any data back to any individual. During the study, if participants sustain an injury they will be instructed to immediately contact the study PIs ([name] or [name]). There will be no program in place to provide compensation for the cost of care for research related injury or other expenses (such as lost wages, disability, pain or discomfort). The participant and/or their insurance will be billed for the medical care they receive for a research injury.

Participants may withdraw from the study at any time at their own request, or they may be withdrawn at any time at the discretion of the investigator or sponsor for safety, behavioral, or administrative reasons. In any circumstance, every effort should be made to document participant's outcome, if possible. The investigator should document the reason for withdrawal and follow-up with the participant regarding any unresolved adverse events.

If the participant withdraws from the study, and withdraws consent for disclosure of future information, no further evaluations should be performed, and no additional data should be collected. The study team may retain and continue to use any data collected before such withdrawal of consent.

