#### **4.6. Safety Summary**

Adverse events (AEs) will be summarized and presented in a table.

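### SAP 3.5 ends adverse-event recording at a qualifying procedure that neither document defines, so the period covered by the only planned safety table is not fixed

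*SAP*

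**What the plan says.** SAP 3.5 gives a broad definition of an AE and then the recording rule: "Any AE that occurs from the time the participant consents to the clinical research through the completion of the qualifying procedure will be recorded". SAP 4.6 is the whole of the safety analysis: "Adverse events (AEs) will be summarized and presented in a table". It names no period.

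The protocol has no AE section and no sentence stating an AE window. Three places bear on timing:

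- Protocol 9 (Consent), on injury: "During the study, if participants sustain an injury they will be instructed to immediately contact the study PIs".
- Protocol 9 again, on withdrawal, which may happen at any time: "The investigator should document the reason for withdrawal and follow-up with the participant regarding any unresolved adverse events".
- Protocol 12 (Monitoring of Study Data) has participants report symptoms related to activity to the investigator, and has the PI review data and procedures monthly.

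The Schedule of Activities (Protocol 1.2) also has an AE/SAE row, but no visit marks for it can be read in the text available here.

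**The concern.** The rule has a clear start (consent) and an end that cannot be located. *Qualifying* most naturally suggests the step that establishes eligibility, and in this study that step is complete at baseline. A window closing there would leave out the intervention.

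That matters because risks named in Protocol 2.3 arise wholly or partly later. On PT itself it says: "In some persons, knee pain could worsen with exercise". It also names skin irritation from continued sensor wear, and soreness that may appear the day after strength testing. If the table shows no event of one of these kinds, a reader needs to know whether none occurred or none was recorded. The SAP as worded does not tell them.

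**Working it through.** The plan gives no figure to reproduce, and no sample-size or error-rate formula applies. The check is a reading of the two documents against the study timeline.

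**Inputs**

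- Start of window: consent, which for most participants is obtained at the baseline in-lab visit in week -1 (Protocol 6a, Informed consent; Protocol 1.2).
- Last eligibility step: "Step 4 will be an in-lab visit (part of baseline visit) to confirm BMI eligibility" (Protocol 6a, Recruitment and screening).
- PT visits: two per week in weeks 1 to 6, then one per week in weeks 7 to 12 (Protocol 6a, Intervention), so 2 × 6 + 1 × 6 = 18.
- Last study activity: at-home sensor assessment in week 19 (Protocol 4.1), so weeks after PT = 19 − 12 = 7.

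**Step 1: locate the term.** The study consists of screening, a baseline visit, PT, lab visits at weeks 6, 12 and 18, and a final week of sensor wear. None is called a qualifying procedure, and the phrase occurs only in SAP 3.5. The sentence there is complete, so this is neither a redaction nor an extraction gap.

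**Step 2: bound the window.** The two extreme readings give:

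| Reading of the end point | PT visits covered | PT weeks covered | Weeks 13–19 covered |
|---|---|---|---|
| Baseline eligibility check (week -1) | 0 of 18 | 0 of 12 | 0 of 7 |
| Last study activity (week 19) | 18 of 18 | 12 of 12 | 7 of 7 |

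**Step 3: test the narrow reading.** For most participants, consent and the BMI check fall at the same visit, so the window would open and close within about one visit. Where COVID-19 prevents an in-lab screening visit, BMI comes from the physician's letter, and the last check need not follow consent at all. The narrow reading also conflicts with Protocol 9, since reporting injuries during the study and following up unresolved AEs at withdrawal both presuppose capture after baseline. Protocol 12 points the same way.

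**Step 4: look for an end point elsewhere.** Protocol 9 and 12 imply continued capture but give no last day. The AE/SAE row of the schedule cannot settle it. Its marks are missing from a broken table, and the sleep-interference and medication rows show none either, although Protocol 6a says "participants will complete daily questionnaires (sleep interference, medication use, exercise and activity log" and so on. SAP 4.6 supplies no period.

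**Step 5: would the phrase end of study be enough?** Not quite. The Visit #1 text in Protocol 6a places the end of the study at week 18 when describing wrist-sensor wear. Protocol 4.1 and the Visit #4 text continue sensor wear for a further week. The replacement should name the week.

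**The case against.** The strongest case against is that this is a drafting slip with little practical effect. The narrow reading is a gloss: the protocol speaks of screening and eligibility, never of a qualifying step. SAP 4.6 applies no window filter, and SAP 4.1.1 bases all summaries on observed data. If the site records AEs throughout, nothing in the SAP removes them from the table. Worsening knee pain would not go uncollected either: KOOS pain and the nominated-activity pain rating are weekly, pain is asked at every PT visit, and SAP 4.3 analyses change in the patient-reported outcomes. Sensor comfort is in the exit survey.

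Most of this stands, and it limits the point. Pain scores are not an AE table, however, and the objection still leaves that table without a stated period.

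A reader might infer three stronger things that the documents do not support:

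- *That AEs will not be recorded during PT.* The narrow reading is a bound, not a forecast, and Protocol 9 and 12 point the other way.
- *That the SAP contradicts a window stated in the protocol.* The protocol states none, and the schedule row is unreadable here. Only the narrow reading conflicts with the protocol, so the end point is best called undefined.
- *That the SAP overrides protocol capture.* Protocol 7.1 says "The analyses described in the approved SAP will be followed if different from what is described in this protocol". That concerns analyses, whereas the SAP 3.5 sentence concerns what is recorded. Its reach over data collection is doubtful.

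**Conclusion.** The concern holds in this form: SAP 3.5 ends AE recording at a term that is undefined and matches no step of the study, so the SAP does not fix the period covered by the only planned safety table. This is more than missing detail. The sentence is an operative rule, and its nearest literal reading excludes the whole intervention.

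The size is the gap between the readings, from none of the PT visits to all of them. Recording throughout is the more likely practice. In that case no events are lost, and what remains is a reported table whose period the SAP does not support.

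The narrow bound assumes that *qualifying* means the baseline eligibility check. The wide bound assumes capture to the final sensor week, which Protocol 9 and 12 imply but do not state. The correction should be made. Nothing on the efficacy side depends on it: no estimate, sample size or error rate changes.

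**What to change.** In SAP 3.5, replace the closing phrase (from *through* up to *procedure*) with: *through the end of week 19 (final sensor wear) or the early termination visit*. State the same window in SAP 4.6. The schedule already provides for an early termination visit, so no new visit is created.

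The cost is one phrase in SAP 3.5 and one sentence in SAP 4.6, with no new data if AEs were recorded throughout. If recording did stop at baseline, rewording cannot recover the events, and the report must say that the table does not cover PT.

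Two additions are optional: splitting the table by period (before PT, PT weeks 1 to 12, weeks 13 to 19) and giving increased index-knee pain its own row. They would aid reading at the price of small cells. With one arm, they would not allow events to be attributed to PT.

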## 4. ANALYSES AND SUMMARIES

### 4.1. General Methods

Data will be summarized using descriptive statistics (number of subjects (n), mean, median, standard deviation, minimum and maximum) for continuous (or near continuous) variables, and using frequency and percentages for discrete variables. Shapiro-Wilk test will be used to assess normality of variables. Non-parametric statistical methods will be used to analyze non-normally distributed variables.

P-values will be generated where appropriate and any p-value < 0.05 will be considered statistically significant. If multiple p-values are generated within an analyses, Benjamini-Hochberg false discovery rate (FDR) correction will be used to determine significance. P-values will be rounded to 3

decimal places and therefore presented as 0.xxx; P-values smaller than 0.001 will be reported as ‘<0.001’.

